Medication-enhanced psychotherapy (MEP) has re-emerged as one of the most exciting areas in the treatment of PTSD. Current work in this area has been driven by the translation of preclinical research of the biology of fear learning and memory into human clinical trials (i.e., d-cycloserine, propranolol, MDMA, yohimbine, methylene blue, rapamycin, hydrocortisone). Cumulative research(Dunlop, Mansson, & Gerardi, 2012) indicates that PE may be improved by administration of medications that target one or more therapeutic mechanisms such as 1) augmenting the biological processes of extinction memory formation (“cognitive enhancer”); 2) disrupting the reconsolidation of feared memories (“memory disrupter”); or 3) enhancing the trust in the therapist by reducing the anxiety of re-engaging with traumatic material (“therapy facilitator”). Ketamine, an FDA-approved anesthetic that blocks glutamate neurotransmission at high anesthetic doses(Moghaddam, Adams, Verma, & Daly, 1997) but that at subanesthetic doses, induces a paradoxical increase in glutamate neurotransmission(Abdallah et al., 2016) has shown to enhance neuroplasticity in mood disorders(Li et al., 2011) and PTSD(Girgenti, Ghosal, LoPresto, Taylor, & Duman, 2017). Ketamine’s putative mechanism (e.g., sustained increase in prefrontal synaptic connectivity) persists beyond its bioavailability(Duman & Aghajanian, 2012) which is translated into a clinical durability that ranges between 7-14 days by a single infusion through 16-26 days by repeated infusions in PTSD (Feder et al., 2014) (Albott et al., 2018) and mood disorders (Murrough et al., 2013) (Shiroma, Johns, et al., 2014). The therapeutic window created by ketamine’s lasting brain effects was recently examined in a MEP study for OCD patients. A single IV ketamine followed by a brief course of CBT (e.g., 10 one-hour exposure sessions) resulted in a 63% response rate(Rodriguez et al., 2016).

A.4. Glutamate Dysregulation in PTSD.

[figure not shown]
The neurobiological model of PTSD has shifted from monoaminergic to a more complex neuroplasticity hypothesis. Glutamate is heavily implicated in learning, memory, experience-dependent forms of synaptic plasticity, such as long-term potentiation (LTP)(Malenka & Nicoll, 1999), and ultimately in the formation of

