7.2) after treatment (Cohen's $d' = 1.85$). Figure 4 showed PCL-5 sub-clusters which significantly decreased after completion of treatment. Regarding depression, Montgomery- Åsberg Depression Rating Scale (MADRS) total score decreased over the course of treatment ($F_{2,62}, 36.70 = 30.17, p < 0.0005$), and was associated with a large effect size ($d' = 4.69$) (Figure 3A). The remission rate for depression defined by MADRS total score ≤ 9 was 62%.

3.3.2. Pilot data suggest that repeated ketamine sustain response of depression and PTSD for short period: Of the 12 individuals in remission from PTSD after the infusion series, the median time to relapse was 41 days with the 50th and 75th percentiles at 41 and 27 days, respectively (Figure 5B). Six individuals (50% of the individuals who remitted; 40% of the total sample) remained in remission throughout the follow-up period. Paired samples t-tests showed that the mean PTSD symptom severity was significantly higher at four-weeks follow-up ($n = 10$), compared to symptoms 24-hours after the sixth infusion ($t = 3.42; df = 9; p = 0.008$). The median time to depression relapse was 26 days with the 25th and 75th percentiles at 34 and 13 days, respectively (severity was also significantly higher at follow-up ($n = 12$), Figure 5A). The mean MDD symptom compared to symptoms 24-hours after the sixth infusion ($t = 5.08; df = 11, p < 0.0005$).

3.3.3. Pilot data suggest repeated ketamine infusion treatment is a tolerable intervention: Side effect were ascertained prior to each infusion, immediately following the infusion (+40 min), and at one (+100 min) and two (+160 min) hours post-infusion (Figure 6). Three participants (18.8%) required beta-blockers to lower blood pressure (systolic blood pressure > 160 mm Hg and/or diastolic blood pressure > 100 mm Hg). Dissociative symptoms peaked immediately after each ketamine infusion (+40 min) and rapidly resolved during post-infusion monitoring. No significant increase in psychotic or manic symptoms were observed. Of note, no veterans experienced a worsening of PTSD symptoms from baseline at any point during the study, despite the known dissociative effects of ketamine infusions.

C. STUDY MILESTONES

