Doses of ketamine	Several studies(Xu et al., 2016) have shown that ketamine doses at 0.5 mg/kg have higher antidepressant and similar adverse effects than lower (e.g., 0.1 mg/kg or 0.2 mg/kg) or higher (e.g., 1.0 mg/kg) doses, respectively. The presence of an inverted U-shaped relationship between dose and response is supported by higher doses of ketamine having no effect inducing mTOR activation(Li et al., 2011). Moreover, a single ketamine at 0.5 mg/kg, and not at 0.2 mg/kg, showed procognitive effects by improving sustained attention and cognitive response control among 71 patients with TRD (Chen et al., 2018). Studies(Feder et al., 2014) (Albott et al., 2018) in PTSD using a single as well as repeated ketamine infusions were dosed at 0.5 mg/kg with rapid, safe but short-lived reduction of PTSD symptom severity.
Interval between ketamine and PE	Ketamine has an elimination half-life is 186 minutes(Clements, Nimmo, & Grant, 1982) with temporary dissociative/psychotomimetic effects observed at doses of 0.5 mg/kg between 40 and 120 minutes posttreatment, which resolve within 240 minutes of administration(Zarate et al., 2006) (Murrough et al., 2013). However, ketamine's putative therapeutic mechanism (e.g., sustained increase in prefrontal synaptic connectivity (Abdallah et al., 2016) (Duman, Aghajanian, Sanacora, & Krystal, 2016)) persists beyond its bioavailability(Duman & Aghajanian, 2012). These lasting physiological brain changes, which is reached within 24 hrs. of treatment, have proved to be a therapeutic window to enhance the outcomes of psychological interventions in pre-clinical and clinical studies (i.e., extinction learning in animal PTSD (Girgenti et al., 2017) model and CBT in OCD(Rodriguez et al., 2016), respectively). Studies in TRD suggested that the peak of antidepressant effects to ketamine occur 24 hours after administration (Zarate et al., 2006)(Zarate et al. 2006a) (Mathew et al., 2010). Moreover, this notion of peak of efficacy following an intravenous ketamine administration is further supported by the temporal overlap of subacute functional network modulation after 24 hours reported by neuroimaging studies (Scheidegger et al., 2012) (Murrough et al., 2015) .

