D.5.1. Eligibility and Baseline Assessment: The Eligibility and Baseline Assessment (EBA) will be accomplished during 1-2 visits over a 7 -day period prior to starting treatment. It will take a total of 3 hours. Provisional diagnosis of PTSD and its severity would be obtained by PCL-5 score >33 . The CAPS-5 would be then administered to establish PTSD diagnosis. The M.I.N.I. International Neuropsychiatric Interview (M.I.N.I. 6.0)(Sheehan et al., 1998) will be used for psychiatric evaluation to confirm the absence of exclusionary diagnoses. Lack of moderate/severe cognitive impairment will be ascertained with an MMSE score ≥ 28 . Evaluation of exclusionary criteria involving unstable medical illnesses will be based on brief physical examination, medical record review by study M.D. in consultation with on-site study

anesthesiologist, basic metabolic laboratory tests, and ECG. A urine pregnancy, if applicable, and drug screen will also be obtained. Secondary outcomes at baseline will include cognitive function (CogState), severity of depressive symptoms (MADRS), levels of anxiety (Beck Anxiety Inventory-BAI), suicide risk (Columbia- Suicide Severity Rating Scale- C-SSRS), pain intensity (Numeric Rating Scale-NSR for pain), clinical impression of illness severity (Clinical Global Impression-CGI) quality of life (World Health Organization Quality of Life-Brief-WHOQOL-BREF), and expectation of treatment (CEQ).

D.5.2. Treatment Assessment: The research staff will measure PTSD symptoms severity by administering the CAPS-5 at weeks 4, 12 and 2-month follow-up. Secondary outcomes that includes cognitive function, anxiety, depression, pain, suicide, and general side effects (Patient Rated Inventory of Side Effects- PRISE/ Frequency, Intensity, and Burden of Side Effects Rating-FIBSER) will be obtained 24 hrs. post-ketamine and prior to PE session at week 1, 2, and 3 (ketamine-PE phase). We will administer rating scales again at week 4, 6, 8, and 12 (ketamine-free phase), and at 2-month follow-up. Fear activation and extinction during PE sessions would be measured by the Subjective Units of Distress Scale (SUDS).

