6.7.3. Data Analysis: The data analyses will be performed by [name], Co-I on this project. Each subject will be assessed for the primary outcome variable (CAPS-5 score) at baseline (1-2 weeks prior to starting the intervention), week 4, and at the end of PE treatment (week 12). *Statistical analysis for this study will be essentially descriptive in nature. We will assess means, standard deviations, and 95% confidence intervals in symptoms at key assessment points. We will also examine distribution of missing data. In addition to the CAPS-5, we will also examine change in our secondary measures (PCL-5, CogState, MADRS, etc.), again these analyses will be descriptive in nature and will be used to refine our RCT proposal.*

6.7.4. Data Safety.

After the recruitment of 6 subjects, an independent, 3-person panel of physicians and researchers will conduct a reassessment of the risks and benefits to study participants. This panel will review all adverse events for severity and frequency.

6.8. Anticipated potential problems and alternative strategies.

The research infrastructure and SOPs to run ketamine infusions, and a well-established PTSD service are currently in place at MVA to assure timely start-up within 3 months. However, possible problems and solutions during execution of the study might be: 1) Slow recruitment/enrollment: We cautiously propose recruiting about 10 veterans aim to complete the primary outcome for our study. Nevertheless, if recruitment is slow, we would expand to include recruitment from satellites clinics within the Minneapolis VA Health Care System. In addition, we could reach out the Veteran's population served at the St. Cloud VA Health Care System (SCVAHCS) (see. 6.3.2. Feasibility of recruitment. 2) Dropouts and missing data: In our own sample, out of 16 subjects, only 2 dropped out in agreement with the literature that consistently supports tolerability of serial ketamine infusions. However, if risk of dropping out due to assessment burden occurs, subjects will have the option of completing a minimum core of primary outcome measures and maintain a flexible routine for recurrent appointments. For missing values, we will handle it by data imputation strategies, by last-

observation-carried-forward, and by the exclusion of dropouts (completers-only analyses); 3) Lost of follow-up: We would initiate outreach procedures and safety checks.

E. STUDY COMPENSATION

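### LOCF in section 6.8 would enter a MADRS rating taken 24 hours after ketamine as the week-12 score of a patient whose last rating is in weeks 1-3

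*Combined protocol and SAP*

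**What the plan says.** Section 6.8, under dropouts and missing data, states: "For missing values, we will handle it by data imputation strategies", by last-"observation-carried-forward, and by the exclusion of dropouts (completers-only analyses". It names no outcome, exempts no visit, and does not say which of the three approaches leads.

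D.5.2 sets the timing of the secondary ratings, which include depression (MADRS, per D.5.1 and D.6.3), anxiety and pain. They "will be obtained 24 hrs. post-ketamine and prior to PE session at week 1, 2, and 3 (ketamine-PE phase"). The next ratings are off drug: "We will administer rating scales again at week 4, 6, 8, and 12 (ketamine-free phase), and at 2-month follow-up". The CAPS-5 is rated at baseline, weeks 4 and 12, and the 2-month follow-up, so it has no 24-hour rating.

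Table 2, in the row on the interval between ketamine and PE, says: "Studies in TRD suggested that the peak of antidepressant effects to ketamine occur 24 hours after administration". Section A.3 gives a "clinical durability that ranges between 7-14 days by a single infusion through 16-26 days by repeated infusions". Section 3.3.2 on the pilot reports: "The median time to depression relapse was 26 days". It also reports that depression was significantly worse at follow-up than 24 hours after the sixth infusion.

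Section 6.7.3 makes the analysis descriptive (means, SDs and 95% confidence intervals) and says the secondary results will be used to refine a later RCT proposal.

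**The concern.** LOCF assumes that the last value seen still describes the patient at the missing visit. For a MADRS rating from weeks 1-3, the plan's own background contradicts this. The rating is timed to the expected peak of a drug effect that the plan describes as short-lived, whereas week 12 is meant to show the state at the end of nine weeks of ketamine-free PE. A patient who responded to an infusion and then left would be scored as holding that response throughout.

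The same rule treats the same patient differently on the primary scale. With no CAPS-5 between baseline and week 4, LOCF carries the CAPS-5 baseline, meaning no change. An early leaver could therefore show no improvement in PTSD and near-peak improvement in depression, purely because of when each scale is scheduled.

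At stake are the LOCF depression summaries at week 4 and later. With 10 patients each record is a tenth of the mean, and these summaries feed the design of the next trial.

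**Working it through.** **1. The plan's own figure.** Section 3.3.2 gives t = 5.08, df = 11, p < 0.0005 for the worsening of depression between 24 hours after the sixth infusion and follow-up (n = 12). A two-sided t test gives p = 0.00035, which agrees.

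**2. How far the value is carried.** Days from a last rating in week w to week 12 = (12 − w) × 7.
- w = 1: 77 days, after one infusion; stated durability 7-14 days.
- w = 2: 70 days, after two infusions.
- w = 3: 63 days, after three infusions; stated durability for repeated infusions 16-26 days.

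Each span exceeds the stated durability and the pilot's 26-day median time to depression relapse. The 2-month follow-up adds about two months more.

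**3. Size of the rebound in the pilot.** Standardised rebound = t/√n = 5.08/√12 = 1.47. The unit is the SD of the pilot's own within-patient change from the 24-hour rating to follow-up.

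**4. Shift in the LOCF mean.** If k of 10 patients have a carried 24-hour value and would have rebounded as in the pilot, shift = (k/10) × 1.47.
- k = 1: 0.15
- k = 2: 0.29

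These are in the same pilot unit. The documents give no SD for that pilot change or for the week-12 MADRS summary in this trial, so the shift cannot be stated in MADRS points or as a fraction of the trial's confidence interval.

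**5. How likely at least one such patient is.** The documents do not say what share of dropout falls in weeks 1-3. Assume 25% to 50%, for which the documents offer no source. P(at least one of 10) = 1 − (1 − d × share)^10, where d is the dropout rate.
- d = 2/16 = 12.5% (the team's own sample, section 6.8): 1 − (1 − 0.03125)^10 = 27% to 1 − (1 − 0.0625)^10 = 48%; expected number 0.31 to 0.63.
- d = 38% (PE arm of the trial cited in A.2): 1 − (1 − 0.095)^10 = 63% to 1 − (1 − 0.19)^10 = 88%; expected number 0.95 to 1.9.

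Neither rate fits exactly. The first comes from ketamine without PE, the second from PE without ketamine. The first is also uncertain because section 3.3.1 says sixteen veterans completed all six infusions, while 6.8 says 2 of 16 dropped out.

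**The case against.** The strongest reply is that little depends on this. LOCF is one of three listed approaches, in a section on contingencies, in a single-arm descriptive pilot with no hypothesis test or decision rule. The primary outcome is not touched. At the team's own dropout rate, the likelier result under the assumed early share is that no patient is affected. Table 2 places symptom exacerbation at session 4, and anyone who gives a rating at week 4 or later carries a ketamine-free value. All of this stands, and it limits the weight of the point. It does not remove the point: no passage stops the 24-hour value from being carried, and a patient who leaves after session 3 but before the week-4 rating is still caught.

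The pilot is also a loose guide to size. It gave six infusions in 12 days, without PE, to veterans with comorbid treatment-resistant depression. A patient leaving here in weeks 1-3 has had one to three weekly infusions, and depression is not required for entry. This stands too.

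A reader might infer three stronger things that the documents do not support:
- **That every secondary scale is carried at peak effect.** The 24-hour peak is stated only for the antidepressant effect. Anxiety and pain are rated at the same time, but no peak is given for them, and D.5.2 does not name the PCL-5 among its 24-hour measures.
- **That the bias always favours the intervention.** It does so for patients who responded and then lost the response. A non-responder who leaves early has no peak to carry.
- **That the shift is a known share of the confidence interval.** That would divide SDs of two different quantities, neither of which is given.

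**Conclusion.** The point holds for the MADRS, for patients whose last rating is in weeks 1-3. As written, 6.8 lets a rating taken at the stated peak of the antidepressant effect stand for the patient's state 63 to 77 days later, although the plan's own durability and relapse figures say the effect fades well before then. Among responders this makes the LOCF depression means at week 12 and follow-up look better than the off-drug state.

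The indicative size is 0.15 or 0.29 SD of the pilot's change score for one or two such patients in 10, if they rebound as the pilot patients did. The chance of at least one is 27-48% at 2/16 dropout and 63-88% at 38%, both on the unsourced assumption that 25-50% of dropout falls in weeks 1-3.

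Nothing here puts the primary CAPS-5 result in doubt. This is a worthwhile, inexpensive correction to one of three listed methods, and no conclusion of the pilot rests on it alone.

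**What to change.** Add a sentence or two to 6.8, along these lines: *Ratings taken 24 hours after an infusion (weeks 1-3) are not carried forward to week 4 or later. In the LOCF analysis of the MADRS, and for consistency of the other scales rated at the same time, a patient with no rating from week 4 onward takes the pre-treatment baseline value. The 24-hour ratings are summarised only at their own visits.*

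This treats the MADRS as LOCF already treats the CAPS-5 for the same patient. It applies to the LOCF analysis only and need not restrict how other imputation methods use the early ratings.

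It needs no new data or visits. The cost is that the LOCF figures become slightly less favourable. Baseline carried forward is also a single-value rule, and it may understate a lasting gain in someone who left early.
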